12.4.4. Safety Analyses

AEs will be coded using the most recent version of the MedDRA and will be grouped by SOC and PT designation. The severity, frequency, and relationship of AEs to investigational product will be presented by SOC and PT groupings. Listings of each individual AE including start date, stop date, severity, relationship, outcome, and duration will be provided. Each AE (based on PT) will be counted once only for a given study subject. If the same AE occurred on multiple occasions, the highest severity will be assumed. Thus, study subjects are not counted multiple times in a given numerator in the calculation of frequencies for a specific AE. C-SSRS reports of suicidality or suicidal ideation will be reported as AEs and analyzed as AEs if the investigator determines after an interview with the subject that the responses are consistent with suicidal ideation or attempt.

Chemistry data, urine drug screen results, pregnancy test results, and alcohol breathalyzer results, will be reported as summary statistics. Vital signs will be presented as summary statistics and change from baseline. The proportions of ECG results considered abnormal and clinically significant will also be provided. CIWA-AR scores will be analyzed similar to the efficacy endpoints: mixed effects models with and without baseline characteristics. In addition, change from baseline (shift tables) will also be presented for clinical laboratory data. The numbers and proportion of subjects who reported CIWA-AR scores ≥ 10 at any time after the start of dosing will be presented.

12.4.5. Compliance and Retention Analyses

Medication compliance, defined as the amount of investigational product taken as a proportion of the total amount prescribed per protocol, will be evaluated for the HORIZANT Extended-Release Tablets and placebo groups. Self-reported compliance with HORIZANT Extended-Release Tablets will be compared against plasma samples having detectable levels of gabapentin. Average amounts of investigational product taken will be reported for the HORIZANT Extended-Release Tablets and placebo groups. The research participation rate, defined as percentage of subjects with complete drinking data, will be compared between treatment groups. Average amounts of investigational product taken will be reported on a weekly basis and across the entire trial duration. In addition, the percentage of subjects discontinuing medication and a listing of the reasons for discontinuation will be provided. Weekly days of attendance at self-help meetings or other professional service providers to help reduce/quit drinking will be presented as summary statistics by treatment group.

12.4.6. PK Analysis

Plasma levels of gabapentin will be presented as descriptive statistics including mean, SD, coefficient of variation, geometric mean, minimum and maximum levels and mean \pm SD will be presented graphically over time. Population PK analyses will be conducted in accordance with a separate PK/PD SAP.

12.4.7. Baseline Descriptive Statistics

Summaries of the characteristics of the subjects in each of the study groups at baseline will be prepared for the mITT, safety, and evaluable analysis sets. Baseline characteristics will be compared between the HORIZANT Extended-Release Tablets and placebo groups using appropriate statistical methods. A summary will be prepared to show dropouts/retention over time in each group, along with the reason for early termination. The number of missing observations will be presented between groups.

12.4.8. Exploratory Analyses

Exploratory analyses of the continuous secondary drinking endpoints, and the WHO 1- and 2-risk level decrease in alcohol consumption endpoints, will employ a multiple imputation method for handling missing weekly drinking data for the mITT population (Hopke et al-2001, Rubin-1976, Rubin-1996, Schafer-1997). Multiple imputation replaces each missing value with a set of "m" plausible values that represent the uncertainty about the right value to impute. The imputation model will include a limited set of variables likely to be associated with missingness on the primary endpoint, excluding treatment assignment. The variables may include but are not limited to site, time and baseline alcohol use. Specification of the variables used in the multiple imputation models will be provided in the SAP.

Analysis of abstinence from alcohol will not employ imputation for missing drinking data.

The percentage of subjects abstinent from smoking will be analyzed only among subjects who smoked at baseline. Analysis will include two treatment time periods of interest: during the last 4 weeks of the maintenance period and over the entire maintenance period. All analyses of this endpoint will be conducted on both a nonimputed and imputed endpoint using the same modeling methods as other dichotomous secondary endpoints. Imputation will proceed such that

any subject with any missing cigarettes per week data during the evaluation periods for this endpoint will be imputed as a smoker.

Blood PEth levels at Week 26 will be compared between treatment groups using analysis of covariance with treatment group, clinical site, and baseline blood PEth level. The proportion of positive samples [a test result > 8 ng/mL - the lower limit of quantitation (LLOQ) of the test] at Week 26 data will be modeled using logistic regression with treatment group, clinical site, and baseline level as covariates provided there are sufficient observed events.

The MINI AUD number of symptoms (identifiers) at Week 26 (covering the last 4 weeks of the maintenance period) will be compared between the treatment groups using analysis of covariance.

Primary and secondary efficacy endpoints will be compared between treatment groups over the entire maintenance period using the same analytic methods described above for these endpoints; in addition, these endpoints will be analyzed with and without imputation. The PSNHDD, percent subjects abstinent from alcohol, and the WHO 1- and 2- risk level decrease endpoints will be analyzed on a weekly and monthly basis; and cumulatively over Weeks 18-25 (last 8 weeks), Weeks 14-25 (last 12 weeks), and over Weeks 10-25 (last 16 weeks).

A number of variables will be tested as potential moderators of the medication treatment effect on the imputed PSNHDD endpoint over the last 4 weeks of the maintenance period (primary endpoint). The potential moderator variables that will be examined include measures suggestive of alcohol withdrawal (i.e., withdrawal question on the MINI for alcohol use disorder, BAI, BDI-II, PSQI total score, POMS total and subscales, ACQ-SR-R total score, and number of days abstinent prior to randomization), severity of alcohol use disorder (i.e., drinks per week [28 days prescreen], years of regular drinking), reducer status (change in baseline drinks per day), alcohol-related treatment goal (total abstinence vs. less than total abstinence), BIS score, and baseline smoking status.

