12.4.3.2. Supportive Secondary Efficacy Endpoints

Supportive secondary efficacy endpoints will also be analyzed based on data during the last 4 weeks of the maintenance period (Weeks 22 through 25), including TLFB and other questionnaire data assessed at Week 26 that reflect data collected during this period. No imputation will be done on any supportive secondary efficacy endpoint.

In general, every continuous secondary efficacy endpoint is analyzed using a repeated measures mixed effects model where subjects are random effects; factors and covariates are fixed effects.

The primary analysis model for all continuous endpoint is:

• Appropriately transformed endpoint = treatment + week + treatment*week + clinical site + baseline equivalent of endpoint + covariates

Covariates for continuous secondary efficacy endpoints include the baseline equivalent of the endpoint, clinical site, treatment, time and the treatment by time interaction. Additional covariates for the secondary efficacy endpoints may include baseline characteristics with a theoretical and/or empirical basis for a relationship with a particular secondary endpoint.

Such characteristics may include, but are not limited to, drinking goal (total abstinence versus less than total abstinence), age, years of regular drinking (age minus age first started drinking alcohol regularly), baseline alcohol craving scale total score. Prior to the unblinding of the data, matrices of correlations between these baseline characteristics and each of the secondary efficacy endpoints, pooled across blinded treatment assignment, will be produced (using Pearson for continuous variables, Spearman for categorical outcomes). Selection of baseline variables to

include as covariates in the models will be based on consideration of the following criteria: at least modest correlation with outcome (i.e., $r \ge 0.20$), and clinical expertise. Each endpoint may have a unique set of covariates. Care is taken to only select a limited number of covariates such that the models are not over fitted.

This primary model will also be applied to the untransformed endpoint.

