Results based on the primary analysis model and the model of the untransformed endpoint will be presented in tabular form. The overall least squares means and least square means for each time point along with the 95% confidence intervals will be presented for the untransformed endpoint only, while two-tailed p-values and Cohen's d will be presented for both the untransformed and transformed data. Inference and Cohen's d will be based upon the results using appropriately transformed data.

Analysis of the dichotomous secondary drinking endpoints, percent subjects with a WHO 1- and 2-level decrease in alcohol consumption (Aubin et al-2015), will be conducted via a fully covaried logistic regression model and contingency table. Covariates for the logistic regression model will be selected using a similar approach as that used for the primary endpoint PSNHDD as described in Section 9.4.2. Fewer covariates for the logistic regression may be used depending upon the number of observed events. No baseline drinking covariate will be employed for the endpoints, as these endpoints already adjust for baseline drinking in their calculation.

Covariates for both of these endpoints will be pre-specified in the SAP.

Analyses of supportive secondary endpoints with imputation for missing data will be performed as exploratory analyses.

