12.5. Determination of Sample Size

The sample size was based on a conservative approach to the results of the randomized, placebo-controlled trial reported by Mason et al (2014). Mason et al (2014) found an effect size for PSNHDD of odds ratio = 2.8 (Cohen's h = 0.48). However, this study was a single site trial and single site trials are known to have greater effect sizes than multi-site trials (Feinn and Kranzler-2005). Taking a conservative approach, we assumed a smaller effect size for the current multi-site trial, an odds ratio = 2.5; (Cohen's h=.34, that occurs given a placebo PSNHDD during Study Weeks 22-25 of 13% and an active study drug PSNHDD of 27%). To achieve 91% power for this trial, given a two-tailed alpha of 0.05, then a sample size of 173 per group (346 total) is needed (Fleiss et al-2003). The estimates of 13% and 27% for placebo and gabapentin, respectively, assumes 15% of the randomized subjects in each treatment group will dropout prior to or during the last 4 weeks of the Maintenance Period, and consequently, these dropouts will be imputed as subjects with heavy drinking days (i.e., treatment failures).

13. Quality Control and Quality Assurance

This study will be conducted under International Conference on Harmonization (ICH) Good Clinical Practice (GCP) guidelines and all applicable regulatory requirements.

Actions to ensure the accuracy and reliability of data include the selection of qualified investigators and appropriate study centers; the review of protocol procedures with the investigator and study personnel prior to study start; the design of suitable source documents with appropriate instructions for use; the internal audit of source data according to GCP and internal procedures to ensure their accuracy, completeness, and verifiability; as well as the periodic site monitoring by the Sponsor's representatives (clinical monitors of Fast-Track Drugs & Biologics, LLC). Written instructions will be provided for collection, preparation, and shipment of blood and plasma samples. Clinical monitors will review source documents and eCRFs for accuracy and completeness during on-site monitoring visits; any discrepancies will be resolved with the investigator, as appropriate.

Significant and/or repeated noncompliance will be investigated and remedial action instituted when appropriate. Failure to comply with remedial actions may result in study site termination and regulatory authority notification.

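### The exploratory multiple imputation must leave out treatment, the term the analysis estimates; with the predictors named, the effect shrinks by about the missing fraction (15% at the planned dropout)

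*Protocol*

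**What the plan says.** Protocol Section 12.4.8 covers the continuous secondary drinking endpoints and the two WHO risk-level endpoints. Their exploratory analyses "will employ a multiple imputation method for handling missing weekly drinking data for the mITT population". The section then sets a rule for the imputation model: "The imputation model will include a limited set of variables likely to be associated with missingness on the primary endpoint, excluding treatment assignment". It gives examples of predictors, "The variables may include but are not limited to site, time and baseline alcohol use", and defers the full list: "Specification of the variables used in the multiple imputation models will be provided in the SAP". So the SAP chooses the predictors, but the protocol has already decided that treatment is not one of them. It gives no reason and does not describe the method as reference-based or deliberately pessimistic.

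The model that receives the imputed data for the continuous endpoints is in Section 12.4.3.2: "Appropriately transformed endpoint = treatment + week + treatment*week + clinical site + baseline equivalent of endpoint + covariates". The WHO endpoints are compared between arms by logistic regression. The same section announces the imputed versions, "Analyses of supportive secondary endpoints with imputation for missing data will be performed as exploratory analyses", and Section 12.4.8 adds for the whole maintenance period that "in addition, these endpoints will be analyzed with and without imputation".

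The only planning figure for missing data is in Section 12.5, which assumes that "15% of the randomized subjects in each treatment group will dropout prior to or during the last 4 weeks of the Maintenance Period".

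**The concern.** An imputation model should contain at least the terms that the analysis model estimates. Here it must omit treatment, and with it treatment by week. A missing value in the active arm is then drawn from the same distribution as one in the placebo arm with the same site, week and baseline. Filling in such values mixes a share of zero effect into the contrast.

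These analyses exist to show whether the un-imputed results hold up once missing data are dealt with. With treatment left out, the imputed result moves towards no effect even when the missing data are harmless. A smaller or non-significant imputed result would then look like sensitivity to dropout when part of the change comes from the imputation rule. An effect that survives would still be credible with predictors of the kind named, because the error is then conservative.

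**Working it through.** **Inputs from the protocol.** Section 12.5: 173 per arm and 15% dropout per arm. The 15% is an assumption and cannot itself be re-derived. The sample size beside it reproduces: 13% against 27% with 173 per arm at two-sided 0.05 gives power 0.906, or 0.910 by the arcsine method, against the stated 91%. Section 12.4.8: predictors site, time and baseline drinking, without treatment.

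**Assumptions.** True effect 0.35 SD, baseline-outcome correlation 0.5, the responder rates below, and every missing fraction other than 15%.

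**Step 1, algebra.** Let the true adjusted effect be δ and the missing fraction m in both arms. Observed subjects contribute δ and imputed subjects contribute 0, so the expected estimate is (1 − m)δ + m·0 = (1 − m)δ. At m = 0.15 this is 0.85 × 0.35 = 0.298.

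**Step 2, simulation.** 2000 trials per setting: 10 sites, missingness depending on baseline drinking, 15 proper Bayesian linear imputations, Rubin's rules, analysis by treatment + baseline + site. Monte Carlo standard error 0.002.

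| Missing | (1 − m) × 0.35 | Treatment excluded | Treatment included |
|---|---|---|---|
| 5% | 0.333 | 0.327 | 0.349 |
| 10% | 0.315 | 0.309 | 0.354 |
| 15% | 0.298 | 0.294 | 0.344 |
| 25% | 0.263 | 0.260 | 0.345 |

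At 15%, 0.294/0.35 = 0.84. A separate simulation with four weekly outcomes, dropout completely at random and a true effect of 0.4 SD gives 0.90, 0.85, 0.73 and 0.64 of the truth at 10%, 15%, 25% and 35% missing. With treatment included, it gives 1.00 at each fraction. With unequal dropout of 15% and 25%, the excluded estimate is about 0.80 of the truth.

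**Step 3, inference at 15% missing.** With treatment excluded, the combined standard error averages 0.103 while the estimates vary with standard deviation 0.086: 0.103/0.086 = 1.20. The oversized error offsets the bias, so 95% interval coverage stays at 95%. Rejection under the true effect is 86% excluded against 91% included; under no effect it is 2.8% against 5.5%.

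**Step 4, richer predictors.** The list is open, so the SAP may add earlier on-treatment drinking. With correlation 0.7 to the outcome, 15% missing and treatment still excluded, the estimates by early effect are:

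- half the late effect: 0.314 (0.90 of truth)
- equal to it: 0.327 (0.93)
- twice it: 0.359 (1.03)

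With treatment included, the values are 0.352, 0.350 and 0.348. The separate simulation, with equal early and late effects, gives 0.94 to 0.96 with treatment excluded.

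**Step 5, WHO-type responder.** Assume 60% against 72%, pooled rate 66%, 15% missing and imputed at the pooled rate. The arms become 0.85 × 0.60 + 0.15 × 0.66 = 0.609 and 0.85 × 0.72 + 0.15 × 0.66 = 0.711. The log odds ratio falls from 0.539 to 0.457, a ratio of 0.85. A simulation at 50% against 65% (500 trials, 10 logistic imputations) gives 0.532 against 0.628 on full data (0.85) with treatment excluded, and 0.613 against 0.623 (0.98) with it included.

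**The case against.** The strongest reply is that nothing decisive rests on these analyses. The primary endpoint counts missing data as heavy drinking. The supportive secondary endpoints have un-imputed main analyses. The gatekeeping in Section 12.4.11 covers only the primary and key secondary endpoints. The error is also on the cautious side with the predictors named, and coverage holds. All of this stands and limits the importance of the point. It does not justify the rule, since the protocol does not present it as a caution.

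Second, the full shrinkage applies to one permitted specification. What is imputed is weekly drinking, so a subject's other observed weeks are natural predictors, and adding them reduces the bias. This also stands, but the bias is not reliably removed, and its direction then depends on how early and late effects compare.

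Third, 15% may overstate the missing weeks. Some of those subjects leave during the final window and supply part of it. Section 11.33 provides for recovery of missed drinking data and telephone interviews after withdrawal. Under Section 11.34, one week of data is enough for the WHO endpoints. The 5% and 10% rows show the smaller effect.

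Fourth, the simulations compare arms on one outcome or on a four-week mean, not with the full repeated-measures model, so they give no size for the bias in treatment by week. That is correct. The algebra in Step 1 applies to each week separately: with baseline-type predictors, each week's contrast is scaled by one minus that week's missing fraction. If dropout accumulates, later weeks shrink more.

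**Conclusion.** The point holds. The protocol itself fixes an imputation model that is incompatible with its analysis model; this is not a detail left to the SAP. With baseline-type predictors the treatment estimate shrinks by roughly the missing fraction: to 0.84–0.85 of the truth at 15%, and about 0.93 and 0.88 at 5% and 10%. With on-treatment drinking added, it lies between 0.90 and 1.03 at 15%. The effect size, correlations, responder rates and other missing fractions are assumptions, but under dropout completely at random the baseline-only shrinkage ratio does not depend on the effect size.

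The reach is limited to the exploratory imputed analyses of the continuous drinking endpoints and the WHO endpoints. It should be corrected, but it does not threaten the trial's main conclusion.

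**What to change.** In Section 12.4.8, replace the clause that leaves treatment out with one that includes treatment and treatment by time in the imputation model, or that imputes each arm separately. If a pessimistic scenario is wanted, declare it as its own reference-based or delta-adjusted sensitivity analysis.

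The cost is one sentence and a programming change before unblinding. Sample size, conduct and the primary test are unchanged. The price is an assumption that cannot be tested: given the observed data, missing subjects follow their own arm's pattern (missing at random). The separately declared pessimistic analysis covers departures from it.

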8.3. Selection and Withdrawal of Subjects

8.3.1. Inclusion Criteria

Subjects must meet each one of the following inclusion criteria in order to be eligible for participation in the study:

- 1. Be at least 21 years of age.
- 2. Have a current (past 12 months) DSM-5 diagnosis of AUD (4 or more symptoms) assessed using the MINI neuropsychiatric interview version 7 (moderate severity, ICD-10-CM Code F10.20 alcohol dependence, uncomplicated).
- 3. If male, report drinking an average of at least 28 drinks per week or if female report drinking an average of at least 21 drinks per week for the 28-day period prior to consent and for both males and females one heavy drinking day per week over the 28-day period.
- 4. Have a BAC by breathalyzer equal to 0.000 when s/he signed the informed consent document (either just prior to or immediately after signing consent).
- 5. Be abstinent (by self report) in the 3-days prior to the day of randomization and have a BAC of 0.000 by alcohol breathalyzer on the day of randomization.

- otocoi Number: NCIG-006
 - 6. Be seeking treatment for problems with alcohol.
 - 7. Be able to verbalize an understanding of the consent form, able to provide written informed consent, verbalize willingness to complete study procedures, able to understand written and oral instructions in English and able to complete the questionnaires required by the protocol.
 - 8. Agree (if the subject is female and of child bearing potential) to use at least one of the following methods of birth control, unless she is surgically sterile, partner is surgically sterile or she is postmenopausal:
 - a. oral contraceptives,
 - b. contraceptive sponge,
 - c. patch,
 - d. double barrier (diaphragm/spermicidal or condom/spermicidal),
 - e. intrauterine contraceptive system,
 - f. etonogestrel implant,
 - g. medroxyprogesterone acetate contraceptive injection,
 - h. complete abstinence from sexual intercourse, and/or
 - i. hormonal vaginal contraceptive ring.
 - 9. Be able to take oral medication and be willing to adhere to the medication regimen.
 - 10. Complete all assessments required at screening and baseline.
 - 11. Have a place to live in the 2 weeks prior to randomization and not be at risk that s/he will lose his/her housing by Study Week 28.
 - 12. Not anticipate any significant problems with transportation arrangements or available time to travel to the study site by Study Week 28.

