8.5. Baseline and Final Eligibility Assessments

If the subject is eligible after performing all the initial screening assessments, s/he will be scheduled to start the study and will come to the clinic for a final eligibility check including the following assessments:

- Alcohol breathalyzer (must have a reading of 0.0 to support abstinence)
- Urine drug screen
- Update medical history
- Update physical exam new symptoms directed exam
- Vital signs
- Weight (if not recorded at the initial screening visit)
- CIWA-AR
- C-SSRS*
- Pregnancy test for females of child bearing potential (must be completed within 2 days of the subject being randomized and dispensed investigational product)
- Birth control methods, if female
- Prior medications update
- TLFB (must report 3 days of abstinence prior to randomization)

An eligibility checklist will be completed and reviewed by a study investigator and, if the subject is still eligible, he/she will complete the following baseline assessments:

- Blood for DNA genomics and RNA expression testing
- Blood spot collection for phosphatidylethanol (PEth) level determination

^{*}Note that the MINI will be used to rule out subjects who attempted suicide in the past year and current (past year) suicidal ideation at initial screening, with the C-SSRS providing an update on current suicidal ideation since screening.

The subject will complete the following questionnaires electronically:

- ACQ-SR-R
- Drinking Goal
- Modified Fagerström Test for Nicotine Dependence
- Smoking Quantity Frequency Questionnaire
- PSQI
- BAI
- BDI-II
- ImBIBe
- Family History of Alcohol Problems
- Barratt Impulsiveness Scale (BIS)
- POMS
- Other Services for Alcohol Use Problems

If the subject reported drinking in the three days prior to randomization, they can be rescheduled for another randomization visit if they agree to try to stop drinking for the required period of 3 consecutive days prior to randomization. The screening period will not be extended. If the investigator determines that the subject could be a viable participant who could not for extenuating circumstances complete the screening period in 14-days, the subject can be rescreened by completing all of the screening assessments again. In this case, the subject will be assigned a new subject number.

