11.23. Phosphatidylethanol Determination

Phosphatidylethanol (PEth) as a biomarker for chronic alcohol use has been reviewed recently by Viel et al-2012). PEth is formed in the blood by hydrolysis of phosphatidylcholine catalyzed by phospholipase D to phosphatidic acid that when in the presence of blood alcohol results in the production of PEth (Mueller et al-1988). In clinical studies conducted on chronic heavy drinkers, PEth was found to be detectable in blood up to 28 days after sobriety (Aradottir et al-2006; Hansson et al-1997; Hartmann et al-2007; Varga et al-1998; Wurst et al-2010; Wurst et al-2012). In 15 alcoholics following a detoxification program, the mean half-life of blood PEth was 4.0 ± 0.7 days with a range of 3.0-5.3 days (Varga et al-2000). It has been demonstrated that sex,

gender, age and body mass index do not influence the normalization rate of PEth (Wurst et al-2010). In a recent experiment during which, after three weeks of abstinence, 11 social drinkers were exposed to an amount of ethanol of 1 g/Kg for five consecutive days (daily alcohol intake ranging between 67 and 109 g/day), and then remained abstinent for 16 days, undergoing regular and scheduled blood sampling, the mean half-life of PEth ranged from 4.5 to 10.1 days in the first week and from 5.0 to 12.0 days in the second week (Gnann et al-2012).

A dried blood spot method will be used by pricking the subject's finger (after wiping with an alcohol swab) with the lancet provided in the collection kit and allowing blood to wick onto the collection card (5 total spots will be collected on the card). The card may be stored at room temperature for up to one year before assay. Cards will be sent periodically during the study to the central laboratory (United States Drug Testing Laboratories, Des Plaines, IL) for analysis.

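### The exploratory Week 26 PEth model leaves out days since last drink, so its baseline covariate carries avoidable noise, with a small loss of precision and no bias

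*Protocol*

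**What the plan says.** - **When baseline PEth is drawn.** Section 8.5 lists "Blood spot collection for phosphatidylethanol (PEth) level determination" among the assessments done after the final eligibility check. Table 5 places the card at Day -1 and again at Week 26.
- **What comes before the draw.** Section 8.3.1 requires subjects to "Be abstinent (by self report) in the 3-days prior to the day of randomization". This sets a minimum of 3 dry days and no maximum.
- **The screening window.** Section 8.5 lets a subject who drank be rescheduled, adds that "The screening period will not be extended", and allows full rescreening of a subject who "could not for extenuating circumstances complete the screening period in 14-days". Fourteen days is thus a limit on screening, not a required length of abstinence.
- **How fast PEth falls.** Section 11.23 cites a mean half-life of 4.0 days in 15 alcoholics after detoxification, "with a range of 3.0-5.3 days". It also cites 4.5 to 10.1 days (first week) and 5.0 to 12.0 days (second week) in 11 social drinkers.
- **The models.** The Week 26 ANCOVA in Section 12.4.8 uses "analysis of covariance with treatment group, clinical site, and baseline blood PEth level". The logistic model for a positive sample uses the same kind of terms, provided there are enough events.
- **The missing variable is available.** Section 12.4.8 lists "number of days abstinent prior to randomization" as a possible moderator of the primary endpoint. It is not in either PEth model.

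**The concern.** A baseline covariate earns its place in an ANCOVA by predicting the outcome. Here it is meant to carry each subject's usual level of drinking. The trial's other baseline drinking measures do this by covering the 28 days before consent or screening. PEth is instead read after a dry interval whose length can differ between subjects, and by the protocol's own half-lives it falls appreciably over that interval. Part of the spread in baseline PEth therefore reflects time since last drink rather than prior consumption.

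The model does not separate the two, although the TLFB supplies what is needed to do so. What is at stake is the precision of one exploratory between-group comparison.

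**Working it through.** The protocol states no PEth effect, power or sample size, so there is no figure to reproduce. The check has three steps.

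**1. Decay by Day -1.** Fraction remaining = 0.5^(days / half-life).

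At 4.0 days:
- 3 dry days: 0.5^(3/4) = 0.595
- 7 dry days: 0.5^(7/4) = 0.297
- 14 dry days: 0.5^(14/4) = 0.088

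Ratio between two subjects with equal prior drinking = 2^(difference in dry days / half-life):

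| Half-life (days) | 3 v 7 dry days | 3 v 14 dry days |
|---|---|---|
| 3.0 | 2.52 | 12.70 |
| 4.0 | 2.00 | 6.73 |
| 5.3 | 1.69 | 4.21 |
| 10.1 | 1.32 | 2.13 |
| 12.0 | 1.26 | 1.89 |

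**2. Share of the variance of log baseline PEth due to dry days.** Two inputs are not in the protocol and are assumed: a between-subject SD of log PEth at last drink (s) of 0.5 to 1.2, and dry days spread uniformly from 3 to an upper limit.

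SD from dry days: s_d = (upper − 3)/√12 × ln 2 / half-life. Share = s_d² / (s_d² + s²).

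- 4.0-day half-life, 3 to 14 days: s_d = 11/3.464 × 0.1733 = 0.55. Shares are 55%, 38%, 27% and 17% for s = 0.5, 0.7, 0.9 and 1.2.
- 4.0-day half-life, 3 to 7 days: s_d = 0.20. Shares are 14%, 8%, 5% and 3%.
- 10-day half-life, 3 to 14 days: s_d = 0.22. Shares are 16%, 9%, 6% and 3%.

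**3. Effect on the treatment comparison.** ANCOVA was simulated 4,000 times per case with 147 subjects per arm (173 less the 15% dropout assumed in Section 12.5) and a true effect of −0.40 outcome SD. Baseline PEth was on the log scale, and the model was fitted with and without days dry. The base case is s = 0.9, correlation 0.5 between log PEth at last drink and outcome, half-life 4 days, and 3 to 14 dry days. The other rows change one input.

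| Case | SE without term / SE with term |
|---|---|
| Base case | 1.043 |
| Correlation 0.3 | 1.015 |
| Correlation 0.7 | 1.114 |
| s = 0.5 | 1.081 |
| s = 1.2 | 1.030 |
| 3 to 7 dry days | 1.007 |
| Half-life 10 days | 1.008 |

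The mean estimate was −0.40 to two decimals with and without the term in every case.

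A closed form agrees. With correlation ρ and k = s²/(s² + s_d²), the SE ratio is √[(1 − ρ²k)/(1 − ρ²)]. In the base case k = 0.81/(0.81 + 0.303) = 0.728, so the ratio is √[(1 − 0.25 × 0.728)/0.75] = √(0.818/0.75) = 1.044. At ρ = 0.7 it is √[(1 − 0.49 × 0.728)/0.51] = 1.12, against 1.11 simulated.

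**The case against.** The strongest reply is that nothing here is invalid. Adjusting for the baseline value of the outcome is standard ANCOVA. The endpoint is exploratory and outside the gatekeeping of Section 12.4.11. Section 12.4.1 leaves covariates to the SAP and already provides for transforming non-normal endpoints. The gain may be only a percent or so of the standard error. All of this stands as a limit on the weight of the point. It does not remove it: Section 12.4.8 names the PEth covariates itself, while it expressly defers the multiple-imputation variables to the SAP.

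Four stronger readings might be inferred, and the protocol does not support them:

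- **That baseline PEth mainly records days since last drink.** At a 4-day half-life the dry-day share passes one half only if the 3 to 14 day range is used evenly and s is below about 0.55. With a 3 to 7 day spread it is 3 to 14%. The longer half-lives in Section 11.23 lower it further.
- **That subjects must be dry for up to 14 days.** Only 3 days are required. Rescheduling inside a fixed window allows many dry periods close to 3 days.
- **That the comparison is biased.** The dry period precedes randomization, so it is independent of arm.
- **That PEth is the only objective check on self-reported drinking.** Breath alcohol is measured at every clinic visit, and GGT repeatedly from screening to the final visit.

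**Conclusion.** The point holds as a minor improvement. Baseline PEth is reduced by a dry period of at least 3 days whose length may vary between subjects, and the Week 26 PEth models ignore that variation although the data to adjust for it are collected.

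The consequence is lost precision only. The SE is about 1 to 4% larger in plausible cases. It is about 8% larger if subjects' PEth levels at last drink are unusually alike (s = 0.5), and about 11% larger if baseline and outcome correlate at 0.7. The loss is under 1% if dry periods run only 3 to 7 days or the half-life is near 10 days.

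These sizes rest on assumed values for the between-subject SD, the distribution of dry days and the correlation, none of which the protocol gives. They also take self-reported dry days as accurate. No confirmatory result is affected.

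**What to change.** In Section 12.4.8, or in the SAP before unblinding, add days since last drink at Day -1 (from the TLFB) to the Week 26 PEth ANCOVA, and enter baseline PEth log-transformed. The two changes belong together: exponential decay is linear in days only on the log scale. Add the same term to the logistic model for a positive sample only if the number of events allows.

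The cost is one degree of freedom, plus a stated convention for baseline values below the assay's 8 ng/mL limit so that the log is defined. No new data are needed, and the sampling schedule stays as it is.
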